1.1 Purpose of National HIV Behavioral Surveillance (NHBS)

Based on a June 1999 review of national HIV prevention programs, CDC's Advisory Committee for HIV and STD Prevention and other external experts called for the development of a national plan for HIV/AIDS prevention. In 2000, CDC, in collaboration with representatives from state and local health departments, academic institutions, and clinical and prevention organizations, initiated a strategic planning process that culminated in the development of CDC's *HIV Prevention Strategic Plan Through 2005*¹. As part of this plan, four national goals were identified to reduce the annual number of new HIV infections in the United States by half. One of these goals, which remains a national priority^{2,3}, was to strengthen the national capacity to monitor the HIV epidemic to better direct and evaluate prevention efforts . In 2002, as an initial step toward meeting this goal, CDC awarded supplemental funds to state and local health departments to develop and implement National HIV Behavioral Surveillance (NHBS)^{4,5}.

NHBS was developed to help state and local health departments establish and maintain a surveillance system to monitor selected behaviors and prevention services among groups at highest risk for HIV infection. Findings from NHBS are used to enhance the understanding of HIV risk and testing behaviors in these groups, and to develop and evaluate HIV prevention programs that provide services to them. Within each participating Metropolitan Statistical Area (MSA), data are collected within the major city or HIV epicenter. Depending on the cycle and sampling method, other areas within the MSA may also be targeted for data collection.

NHBS activities are implemented in rounds composed of three cycles. The first cycle of each round focuses on men who have sex with men (MSM), the second cycle focuses on persons who report injection drug use (IDU), and the third, on heterosexuals at increased risk of HIV infection (HET). These cycles are repeated in rounds so that data are collected from each risk group every three years. Cycles are referred to by the group of interest (NHBS-MSM, NHBS-IDU, and NHBS-HET), and the round of data collection is indicated by a number following the group of interest (e.g., NHBS-MSM1, NHBS-MSM2, etc).

This protocol covers NHBS activities among transgender women, otherwise known as NHBS-Trans. Transgender women (referred to throughout this protocol as trans women) were included as an optional population for data collection in the NHBS funding opportunity announcement 16-1601; NHBS project areas submitted applications to collect additional data among trans women. While individuals have their own conception and understanding of gender, for the purposes of these activities, trans women are defined as individuals who were assigned a male sex at birth and who now consider themselves women, female, or trans women.

NHBS Round 5 Model Surveillance Protocol 1-1 Version Date: October 23, 2017

Timeline and Scope of Protocol 1.2

To date, NHBS has completed four rounds of data collection for core NHBS populations, and the fifth round began in January 2017 with the NHBS-MSM5 cycle. NHBS-Trans will begin in 2018. The activities described in this protocol are for the NHBS-Trans cycle.

Collaborating Agencies 1.3

NHBS-Trans activities were included as part of the existing NHBS cooperative agreement (RFA-PS16-1601). Funding for NHBS-Trans was provided to CDC through the Secretary Minority Initiative Fund (SMAIF). Of the 22 funded NHBS health departments, 13 applied to participate in NHBS-Trans. Those applications were reviewed and scored by a CDC objective review panel based on the applicants' previous experience with surveillance or research activities among trans women, ability to partner with organizations serving trans women, and ability to meet sample size, including the estimated number of trans women in the jurisdiction. Funding is recommended for the top 7 scoring applicants (i.e. the grantees) to conduct NHBS-Trans in the following cities:

- Atlanta, GA (grantee: Georgia Department of Public Health)
- Los Angeles, CA (grantee: Los Angeles County Department of Health)
- San Francisco, CA (grantee: San Francisco Department of Public Health)
- New Orleans, LA (grantee: Louisiana Office of Public Health)
- New York City, NY (grantee: New York City Department of Health and Mental Hygiene)
- Seattle, WA (grantee: Washington State Department of Health)
- Philadelphia, PA (grantee: Philadelphia Department of Public Health)

Together, these 7 cities accounted for over 24% of all persons living with HIV at year end 2012 in the U.S.⁶

1.4 Responsibilities

CDC investigators are principally responsible for developing the protocol and supporting appendices, and for providing technical assistance to the project sites. NHBS project site investigators are to 1) contribute to protocol development, 2) successfully implement the project using the methods described, and 3) ensure submission of data to CDC in a timely manner.

1.5 **Justification for NHBS-Trans**

The ongoing and systematic collection and analysis of data is needed to identify baseline risk behaviors and prevention service utilization, as well as to measure progress toward meeting prevention goals. NHBS-Trans will provide data on the sexual and drug-use behaviors that place trans women at risk for HIV infection, as well as provide data on their use of HIV prevention

services. These data will also provide valuable information for monitoring and evaluating national HIV prevention goals^{2,3} and for guiding national and local HIV prevention efforts. Furthermore, NHBS-Trans data may be used by public health officials and researchers to identify HIV prevention needs, allocate prevention resources, and develop and improve prevention programs directed to the populations of interest and their communities.

Although HIV behavioral surveillance data cannot be used to evaluate the efficacy of specific interventions, they are important for monitoring whether HIV prevention efforts are reaching atrisk populations within a community and whether these efforts meet national and local prevention goals. At the individual level, NHBS-Trans participants may benefit directly from HIV prevention counseling, knowledge of their HIV status, and referrals for additional HIV risk information and care. Participants who have preliminary HIV positive or confirmed HIV positive test results will be counseled and referred for treatment and case management services.

Trans women are at high risk for HIV infection. HIV prevalence estimates in this population have varied, ranging from 3% to 60% for self-reported HIV infection; 16% to 68% for laboratory-confirmed HIV infection. Compared with white trans women, HIV prevalence estimates are higher among African American or black (hereafter referred to as black) trans women. Factors contributing to HIV infection among trans women include condomless sex, survival sex, injection drug use, hormone and silicone injection, unstable housing, and depression and anxiety. In addition, trans women often face barriers to healthcare, including lack of health insurance and lack of culturally competent healthcare providers, that can increase risk for HIV and hinder HIV treatment.

1.6 NHBS Objectives

NHBS contributes to the nation's program of HIV surveillance by being the only multi-site population-based system that provides estimates on key HIV prevention measures among high-risk HIV-negative individuals, HIV-positive individuals unaware of their infection, and HIV-positive individuals aware of their infection who are in and out of care. Accurate and precise data on the behaviors in these populations are critical for tracking the epidemic, planning effective responses, and monitoring and evaluating those responses.

The objectives of NHBS-Trans are designed to monitor behaviors that place trans women at risk for HIV infection. The objectives are as follows:

Seroprevalence

- Assess the prevalence of HIV infection.
- Assess the prevalence of STI infection (where appropriate, if funding is available)

Risk Behaviors

• Assess the prevalence of risk behaviors and social determinants that increase the risk of HIV acquisition and transmission, including:

sexual risk behaviors

NHBS Round 5 Model Surveillance Protocol 1-3 Version Date: October 23, 2017 drug-use risk behaviors

HIV Testing and Treatment

• Describe utilization of HIV testing, linkage to care, and antiretroviral therapy

Prevention

- Assess exposure to and use of prevention services.
- Identify gaps in prevention services and missed opportunities for prevention interventions.

1.7 **General Approach for NHBS Implementation**

NHBS cycles are cross-sectional surveys of persons at increased risk of HIV infection. The survey method used to recruit participants is Respondent Driven Sampling (RDS). RDS has been found effective for recruiting populations that are "hidden". We refer to hidden populations as those for which no sampling frame exists or whose members engage in stigmatized or illegal activities, making them reticent to divulge information that may compromise their privacy. Trans women are an example of a hidden population.

Participants receive tokens of appreciation for participating in NHBS activities. The token of appreciation amounts are determined locally by the NHBS project sites, and are based on previous experience with NHBS cycles or other similar studies. The token of appreciation is for the time required to complete the survey and for providing specimens for HIV testing. The average amount of these tokens of appreciation is \$25 for the survey and \$25 for HIV testing.

RDS, a chain-referral sampling strategy similar to snowball sampling¹¹, is used to recruit trans women that are connected by strong social networks and ties. RDS methods have been widely employed by public health officials and researchers to sample persons at increased risk for HIV for purposes of developing and evaluating HIV/AIDS interventions and for conducting behavioral surveillance. 12 RDS was used to recruit minority trans women in a 2009 CDC pilot, and was an effective sampling strategy. 13 RDS implementation begins with a limited number of initial recruits, or "seeds." Seeds can be identified by persons who work with the target populations or through outreach. People who work with these target populations may be able to appropriately identify dynamic individuals and refer them to the NHBS project staff. If outreach is used to identify seeds, the NHBS project staff should have an informal conversation to determine if the person meets the characteristics of a good seed. Seeds complete the surveillance activities, which include the eligibility screener, the survey, and an optional HIV test, and then are asked to recruit a specified number (up to 5) of people they know. These persons, in turn, complete the surveillance activities and are asked to recruit others. This recruitment process continues until the sample size has been reached. Participants receive tokens of appreciation for recruiting others; the average amount of recruiter tokens of appreciation, based on comparable amounts used in similar studies in these cities, is \$10 per eligible participant who completes an interview.

By starting with a small number of seeds, limiting the number of individuals each participant can recruit, and allowing a significant number of recruitment waves to occur, study investigators assemble a final sample that resembles the underlying eligible population living in the project area and is unbiased by the characteristics of the seeds. 11,14

Sample Size 1.8

Because NHBS is largely descriptive, power calculations, which are done for studies that are primarily designed to test specific hypotheses, were not performed. However, the sample size of 200 eligible respondents per each project site was determined by considering the presumed number of trans women in each city and desired standard error for key indicators of interest (see Chapter 7, section 1), as well as the efficiency of the sampling method used, termed the design effect. This approach has been presented by Salganik¹⁵ to calculate sample sizes for RDS. The sample size calculation recommended for estimating the prevalence of a trait with a given precision is:

$$n = deff \cdot \frac{P_A(1 - P_A)}{(se(P_A))^2}$$

where deff is the design effect and PA is the prevalence of the trait. Analyses of NHBS-IDU data suggest that a design effect approaching 4 is appropriate for RDS studies¹⁶. If we assume a maximally-conservative estimated prevalence for any indicator -0.5 – and a design effect of 4, then a sample size of 200 is adequate to detect such indicators with adequate precision (no greater than 0.1).

The target sample size for each project site, exclusive of "seeds," is 200 completed interviews with participants who meet NHBS-Trans definition inclusion criteria (see Chapter 4, section 2). Across the 7 participating project sites, this would result in a combined sample size of 1,400 trans women.

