3.1 Data Collection Instruments

3.1a Network Questions

Information about the size and characteristics of participants' networks, and descriptions of the relationships between the participant and the person who gave them the coupon, will be used to account for sources of bias inherent to the RDS method and to calculate population estimates and sample variances. A "network" for RDS is defined as those persons whom the participant knows and has recently interacted with, and who meet the eligibility criteria for the given study. A participant's personal network size is based on how many people they know who fit the eligibility criteria for the current NHBS-Trans cycle. Questions to obtain necessary network data are included as part of the NHBS-Trans questionnaire, following the eligibility screener (see Appendix E).

Development of the Network Questions

The network questions used during previous NHBS cycles were developed based on consultation with [name] (the developer of the RDS method), experiences during previous cycles, consultation with NHBS principal investigators, and cognitive testing of the previous questions used in NHBS conducted by the National Center for Health Statistics. The network questions for NHBS-Trans are based on previous NHBS network questions and lessons learned from development, testing, and use of those questions.

3.1b Questionnaire

Questionnaire components

The NHBS-Trans questionnaire consists of two components. First, the core NHBS-Trans questions constitute a standardized main component and are based on the standard questionnaire used for all NHBS populations. Second, participating NHBS-Trans project sites may develop and add questions that address topics of local interest.

Core Questions. The core questions will be used by all project sites participating in NHBS-Trans and will provide data that will be used for comparisons of risk behaviors and HIV testing behaviors of the population of interest between the MSAs. The core questionnaire covers the following areas:

- Demographics
- Sexual behaviors
- Alcohol and drug use history
- HIV testing and prevention experiences
- Health conditions
- Assessment of prevention activities (i.e., exposure to HIV behavioral interventions)

3-1

Local Use Questions. Project sites may include additional questions on topics of local interest. The local use questions shall not exceed 10 minutes maximum for administration.

Development of the questionnaire

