7.1 Data Analysis and Dissemination

CDC will have principal responsibility for analyzing and disseminating multi-site survey data. CDC will also have principal responsibility for analyzing multi-site data on HIV prevalence. The CDC analyses will focus primarily on questions related to the objectives of this project described in Chapter 1. To examine the key behavioral outcomes, data will be weighted when possible to account for the complex sampling design.

NHBS project sites are required for to produce at least one report (fact sheets, epidemiologic profiles, surveillance reports, peer-reviewed manuscripts or other formats as appropriate) and conduct at least one presentation to community partners and stakeholders. Project sites are encouraged to establish Community Advisory Boards (CABs) or other organizations to transmit project findings to the community and stakeholders within the community.

7.1a Outcomes and minimum meaningful differences

Anticipated outcomes for this project vary by population of interest and include:

- Prevalence of HIV risk behaviors;
- Prevalence and frequency of HIV testing, early linkage to care, and receiving antiretroviral therapy
- Receipt of HIV prevention services; and
- Prevalence of HIV infection, including awareness of HIV infection.

7.1b Anticipated products

Each NHBS cycle will result in national and local products and publications. CDC will disseminate national reports, usually via *CDC HIV Surveillance Reports* and other CDC reports, the *Morbidity and Mortality Weekly Report (MMWR)*, and peer-reviewed journals. CDC will also present results at national conferences and meetings. Local NHBS-Trans project sites are expected to disseminate local results to health department officials and the public by presenting results from NHBS-Trans at conferences, preparing reports for community planning groups, or publishing the results in peer-reviewed journals. NHBS-Trans project sites and CDC may collaborate on articles and reports when appropriate.

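### Section 1.8's standard error of at most 0.1 holds for full-sample indicators but not, at city level, for key indicators measured only in HIV-positive women when HIV prevalence is below 50%

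*Protocol*

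**What the plan says.** Protocol Section 1.8 explains that no power calculation was done because the work is largely descriptive. The size per site came from the presumed number of trans women in each city, the standard error wanted for the key indicators (with a cross-reference to Chapter 7, section 1) and the design effect. The formula given is n = deff × P(1 − P) / se².

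The inputs are a design effect of 4, because "a design effect approaching 4 is appropriate for RDS studies", and the instruction to "assume a maximally-conservative estimated prevalence for any indicator -0.5". The conclusion is "then a sample size of 200 is adequate to detect such indicators with adequate precision (no greater than 0.1").

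The cross-referenced list, Section 7.1a, includes "Prevalence and frequency of HIV testing, early linkage to care, and receiving antiretroviral therapy" and "Prevalence of HIV infection, including awareness of HIV infection". Section 1.5 reports earlier estimates of HIV prevalence in this population of "16% to 68% for laboratory-confirmed HIV infection".

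**The concern.** The precision claim is worked out for a denominator of 200, yet it is tied to a list of key indicators that do not all have that denominator. Linkage to care, antiretroviral therapy and awareness of infection are meaningful only among women who are HIV-positive. Section 1.8 makes no allowance for the smaller group.

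This matters because the claim is the only quantitative justification for 200 per site, and these indicators belong to the objectives in Section 1.6. Someone using a city's care or awareness estimate could take it to have a standard error of 0.1 or less when, on the protocol's own inputs, it may be nearly twice that.

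**Working it through.** **Inputs from the Protocol.** Section 1.8: n = 200 per site excluding seeds, 7 sites (1,400 in all), deff = 4, P = 0.5, limit 0.1. Section 1.5: laboratory-confirmed HIV prevalence 16% to 68%.

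**Assumptions not in the Protocol.** The design effect of 4 applies unchanged to the HIV-positive subgroup. Every participant is tested; testing is voluntary and no uptake rate is given, so this is the best case.

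**Step 1: the protocol's own figure.** Rearranged, se = √(deff × P(1 − P) / n).
- At n = 200: √(4 × 0.25 / 200) = √(1/200) = 0.071, which is within 0.1.
- The 95% half-width is 1.96 × 0.0707 = 0.139, or 13.9 points.
- The full-sample claim therefore reproduces. The smallest n that meets se = 0.1 is 4 × 0.25 / 0.01 = 100, so 200 is sufficient with room to spare.

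**Step 2: HIV-positive-only indicators, per city.** Let m be the number HIV-positive among 200. With deff 4 and P = 0.5, se = √(1/m), so se ≤ 0.1 needs m ≥ 100, that is, prevalence of at least 100/200 = 50%.

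| HIV prevalence | m of 200 | se | 95% half-width (points) |
|---|---|---|---|
| 16% | 32 | 0.177 | 35 |
| 25% | 50 | 0.141 | 28 |
| 40% | 80 | 0.112 | 22 |
| 50% | 100 | 0.100 | 20 |
| 68% | 136 | 0.086 | 17 |

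The limit is missed from 16% up to just under 50% and met from 50% to 68%.

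**Step 3: sensitivity to the design effect.** With a subgroup design effect of 2, se = √(0.5/m):
- 16%: √(0.5/32) = 0.125
- 25%: √(0.5/50) = 0.100

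The limit would then be missed only below 25%.

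**Step 4: sensitivity to P.** With deff 4, se ≤ 0.1 requires P(1 − P) ≤ 0.01 × m / 4.
- 16%: P(1 − P) ≤ 0.08, met for P ≤ 0.088 or P ≥ 0.912
- 25%: P(1 − P) ≤ 0.125, met for P ≤ 0.146 or P ≥ 0.854
- 40%: P(1 − P) ≤ 0.20, met for P ≤ 0.276 or P ≥ 0.724

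**Step 5: pooled over the 7 cities.** With deff 4 and P = 0.5:
- 16%: m = 1,400 × 0.16 = 224, se = √(1/224) = 0.067
- 68%: m = 1,400 × 0.68 = 952, se = √(1/952) = 0.032

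Pooled estimates meet 0.1 across the laboratory-confirmed range.

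**The case against.** The strongest reply is that Section 1.8 contains no arithmetic error. It applies the formula to 200 people and gets a correct result, and its reference to any indicator qualifies the assumed prevalence, not the denominator. No sentence promises 0.1 within the HIV-positive subset. The failure is also conditional: it needs prevalence below 50%, a proportion not far from 0.5, and a design effect carried into a subgroup for which the Protocol gives none. National estimates, for which CDC has principal responsibility, are precise enough when pooled.

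Most of this stands, and it limits the point. It does not remove it. Section 1.8 itself ties the calculation to the Chapter 7 list, and that list contains HIV-positive-only outcomes. The value 0.5 is the Protocol's own planning choice. A design effect of 2 still misses the limit at 16%. Pooling helps the national estimates but not the city estimates that sites are expected to disseminate.

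It is also fair to say that linkage and treatment could be asked of women who report being HIV-positive, so incomplete test uptake need not shrink those denominators; it does bear on awareness. Self-report does not rescue precision: the range in Section 1.5 for self-reported infection starts at 3%, which is 6 of 200.

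Three stronger readings are tempting, and the Protocol does not support them.
- A reader might take 0.1 as a 95% margin of error, for which n = 4 × 0.25 × (1.96/0.1)² = 384.1, so 385, would be needed. But the text speaks of a standard error and the formula has no normal multiplier. Even on that reading the claim would not fail for every indicator: at n = 200 the half-width is 0.10 or less for P ≤ 0.154 or P ≥ 0.846.
- Section 3.1b promises "data that will be used for comparisons of risk behaviors and HIV testing behaviors of the population of interest between the MSAs", and a reader might infer that 200 per city is too few for this. Section 1.8 disclaims power calculations and no detectable difference is stated, so no stated figure is contradicted.
- A reader might infer that imprecise city estimates should be withheld. That would work against the project's local-reporting purpose, and nothing here requires it.

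**Conclusion.** The point holds in a limited form. Section 1.8's claim is correct for indicators measured in the full sample. It is not correct at city level for awareness, linkage to care and antiretroviral therapy when fewer than 100 of the 200 are HIV-positive, a condition that covers the cited range from 16% to just under 50%.

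Across the whole cited range the city-level standard error for these indicators is about 0.09 to 0.18. That rests on deff 4 in the subgroup, P = 0.5 and full test uptake. A smaller subgroup design effect or a proportion far from 0.5 would improve it; refusal of testing would worsen it for awareness. This is a stated property that the design lacks for some of its named key indicators. It is not a miscalculation of n.

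**What to change.** Reword the precision statement in Section 1.8 so that it:
- labels 0.1 as a standard error;
- limits the claim to indicators measured in all participants, with a standard error of 0.071 and a 95% half-width of 13.9 points at P = 0.5 and deff 4;
- states that indicators measured only in HIV-positive participants have a city-level standard error of about 0.09 to 0.18 (95% half-width about 17 to 35 points), assuming the same design effect, P = 0.5 and full test uptake, over the cited 16% to 68%;
- states that, on the same assumptions, these indicators meet 0.1 across that range only when pooled over the 7 cities (standard error about 0.03 to 0.07).

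City estimates may still be reported, with their intervals. The change is to wording only and needs no extra participants. Its cost is that the stated precision becomes less favourable. Meeting 0.1 in each city by recruitment instead would take 100/0.16 = 625 interviews at 16% prevalence, 400 at 25% or 250 at 40%, which is not proposed.
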